Also, there are data suggesting SGLT2i acts by inhibiting hepcidin, which will increase iron bioavailability and red blood cell production (13). **Another mechanism is suggested via inducing medullary hypoxia which by turn increases the level of hypoxia inducible factor (HIF) and increase erythropoietin production (14).** These effects on erythropoiesis suggest that the use of SGLT2i reduces the occurrence of anemia. The post-hoc analysis of the CREDENCE trial found that the risk of anemia or the risk of starting anemia treatment in the anemia group of patients with type 2 diabetes and chronic kidney disease was significantly lower than that of the placebo group (15). According to the exploratory analysis of EMPA-REG test data, anemia improvement during SGLT2i treatment was closely related to beneficial cardiovascular outcomes (16).

Dapagliflozin, as a member of SGLT2i family, showed a beneficial effect on cardiovascular outcome (17, 18). As shown in many other trials, Other SGLT2 inhibitors have shown favorable cardiovascular effects, including a reduction in the risk

of hospitalization for heart failure, predominantly in patients with type 2 diabetes and established cardiovascular disease (19-21).

SGLT2 inhibition affects visceral adiposity, glycemic control, hyperinsulinemia, blood pressure, arterial stiffness, and albuminuria (22). Two mechanisms have been proposed as major drivers for beneficial cardiovascular outcome: the diuretic effect associated with SGLT2 inhibition with subsequent hemodynamic unloading of the left ventricle (23) and a shift in cardiac metabolism secondary to increased ketogenesis (24, 25).

Aim of the work

This study aims to:

1. Assess SGT2i role in delaying the progression of ongoing chronic kidney disease.
2. Investigate SGLT2i impact on anemia improvement among non-diabetic CKD patients.
3. Study the impact of SGLT2i on cardiovascular system in these patients.

Research questions

The main research question is: Does use of SGLT2i will show superiority over conventional lines of treatment of chronic kidney disease as regard to efficacy and safety?

Does the use of SGLT2i carry beneficial effect on anemia improvement among these patients?

Does the use of SGLT2i improve cardiac outcome in non-diabetic CKD patients?

Rationale and justification

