Dapagliflozin which was originally developed to control blood glucose level in patients with diabetes has recently been shown to have beneficial effects on both the heart and kidney.

Importantly, a large clinical trial has shown dapagliflozin reduced kidney problems. From the way we think the pills work, there is good reason to believe this new medication could benefit people who have kidney disease even they are not diabetic.

To date, there hasn't been a trial that studied the effect of dapagliflozin in terms of anemia improvement only on non-diabetic CKD.

Objectives

The main objective of this study is to:

- Compare use of SGLT2i versus placebo and standard care in regression of chronic kidney disease in non-diabetic CKD patients.
- Study the effect of SGLT2i in decreasing the risk of anemia and improving anemia in non-diabetic CKD patients.
- Study the impact of SGLT2i regarding cardiovascular system.

Hypothesis

Additional therapies to slow kidney function decline are highly desired. The DAPA-CKD trial demonstrated that the sodium glucose co-transporter 2 inhibitor dapagliflozin significantly reduced the risk of kidney failure and prolonged survival in participants with chronic kidney disease with and without type 2 diabetes.

Patients and methods

Study sitting: Urology and Nephrology Center, Mansoura University.

Study design and sample size:

- **Sample size:** was calculated based on previous research by (DAPA-CKD) by (Heerspink et al., 2020) using G. power program with α error 0.05 and power 80% and it was equal to approximately 98 patients.

Type of the study: Randomized controlled trial.

Patients' enrollment: 100 patients with non-diabetic CKD with an estimated glomerular filtration rate (eGFR) of 20-75 ml/min/1.73m² will be randomized into 2 equal groups:

- **Study group:** 50 patients will receive SGLT2i as add on drug, Dapagliflozin 10 mg will be used once daily with or without food.
- **Control group:** 50 patients will receive placebo beside the conventional medications.

All patients will be followed-up for 12 months and their results will be interpreted.

Inclusion criteria:

1. Non-diabetic CKD patients aged more than 18 years.
2. Patient with eGFR > 20 ml/min/1.73m² by 2021 CKD-EPI creatinine equation

Exclusion criteria:

1. eGFR < 20 ml/min per 1.73 m².
2. Medical history of chronic disease (diabetes mellitus, chronic liver disease, bladder cancer, severe respiratory distress).

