3. Evidence of urinary obstruction or difficulty in voiding at screening.
4. Receiving high dose diuretics or combined ACEI and ARB.
5. History of recurrent urinary tract infection.

6. Active infection including TB and HIV.
7. Current or previous organ transplantation or expected to get a kidney transplant within 12 months.
8. Patients who are on SGLT2i for more than the preceding 3 months.

Study design:

Study Protocol:

- Patients included in the study will be treated with dapagliflozin initiated at a single daily morning dosage of 10 mg/day.

Methods:

The following data will be collected and evaluated for all patients:

I-Baseline investigations:

- Patients of both groups will be subjected to full history taking including duration of CKD and drug history and routine clinical examination.
- Ankle/brachial pressure index (ABPI) to assess peripheral vascular disease.

➤ Laboratory investigations:

- 1) Serum creatinine, Creatinine clearance.
- 2) Urine analysis.
- 3) 24-hour urine protein and/or spot urine protein/creatinine ratio.
- 4) Random blood glucose.
- 5) Lipid profile
- 6) Iron profile tests:

- Hemoglobin
- Mean corpuscular volume (MCV) and Hematocrit (Hct).
- Serum ferritin
- Transferrin saturation (TSAT)
- Serum hepcidin level
- Serum erythropoietin level.

7) B-type natriuretic peptide (BNP) level.

➤ **Cardiovascular investigatory tools:**

- Electrocardiography (ECG).
- Echocardiography to assess myocardial function.

➤ **Radiological investigations:**

- Agatston score using CT scan: for assessment of coronary calcification.

1. II-Post-intervention investigations:

All patients will be evaluated every visit (every 3 months) regarding:

- Regular measurement of blood pressure each visit.
- Ankle/brachial pressure index.
- Laboratory investigations:
 - 1) Serum creatinine, creatinine clearance.
 - 2) Urine analysis.
 - 3) 24-hour urine protein and/or spot urine protein/creatinine ratio.
 - 4) Fasting blood glucose.
 - 5) Lipid profile.

6) Iron profile (Hemoglobin, MCV, hematocrit, ferritin, TSAT,)

All patients will be evaluated at 12 months regarding:

➤ Ankle/brachial pressure index.

➤ **Laboratory investigations:**

1) Serum creatinine, Creatinine clearance.

2) 24-hour urine protein and/or spot urine protein/creatinine ratio.

3) Urine analysis.

4) Fasting blood glucose.

5) Lipid profile.

6) Iron profile tests:

- Hemoglobin
- Mean corpuscular volume (MCV) and Hematocrit (Hct).
- Serum ferritin
- Transferrin saturation (TSAT)

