- Serum hepcidin level
- Serum erythropoietin level.

➤ **Cardiovascular investigatory tools:**

- Electrocardiography (ECG).
- Echocardiography to assess myocardial function.

➤ **Radiological investigations:**

- Agatston score using CT scan: for assessment of coronary calcification.

Outcomes:

Primary outcome measures:

- Time to the first occurrence of any of the components of the composite:
≥50% sustained decline in eGFR, reaching end-stage kidney disease.
[Time Frame: 12 months]

Secondary outcome measures:

- Effect of Dapagliflozin on eGFR.
- Effect of Dapagliflozin on anemia & erythropoietin level.
- Effect of Dapagliflozin on myocardial function and coronary calcifications.
- Safety of Dapagliflozin regarding the number of hypoglycemia episodes between groups and serious adverse events.

Statistical Analysis:

Qualitative data will be displayed in cross tabulations, and quantitative data will be described in terms of arithmetic mean \pm SD. Bivariate techniques will be used for initial evaluation of contrasts. Thus, the chi-square and Fisher's exact tests will be used for comparisons of frequencies of qualitative variables; the Mann-Whitney test and the unpaired t-test will be used for comparisons of means of two quantitative variables. A p-value ≤ 0.05 is considered significant. Patient survival rates will be assessed using the Kaplan-Meier method. All analyses will be carried out using the computer package SPSS for windows, release 21 SPSS Inc. Chicago, III, USA.

Administrative design

All the patients provided written informed consent before study entry and the approval was obtained from institutional review board (MS.22.04.1973) in Faculty of Medicine, Mansoura University. There is no funding.

References

1. Eckardt, K. U., Coresh, J., Devuyst, O., Johnson, R. J., Köttgen, A., Levey, A. S., & Levin, A. (2013). Evolving importance of kidney disease: from subspecialty to global health burden. *The Lancet*, 382(9887), 158-169.
3. Silver, S. A., Bell, C. M., Chertow, G. M., Shah, P. S., Shojania, K., Wald, R., & Harel, Z. (2017). Effectiveness of quality improvement strategies for the management of CKD: a meta-analysis. *Clinical Journal of the American Society of Nephrology*, 12(10), 1601-1614.

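### No recording of ESA, iron or transfusion is specified after baseline, and no handling of them in the anaemia outcome, so the erythropoietin and iron-marker contrasts could not be interpreted

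*Combined protocol and SAP*

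**What the plan says.** Anaemia is one of three items under Objectives: "Study the effect of SGLT2i in decreasing the risk of anemia and improving anemia in non-diabetic CKD patients". Under Outcomes it becomes a secondary measure, "Effect of Dapagliflozin on anemia & erythropoietin level", with no variable, time point or definition of anaemia.

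The Introduction gives the biological case, that the class works by "inhibiting hepcidin, which will increase iron bioavailability and red blood cell production". It also cites a post-hoc analysis of another trial, in type 2 diabetes with CKD, in which "the risk of anemia or the risk of starting anemia treatment" was lower than on placebo.

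On co-treatment the text is thin:

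- **Background care (Patients' enrollment).** "50 patients will receive placebo beside the conventional medications". These medications are not listed. The exclusion criteria do not mention ESA, iron or transfusion.
- **Baseline (Methods, section I).** "full history taking including duration of CKD and drug history and routine clinical examination".
- **Every 3 months (Methods, section II).** Blood pressure, ankle/brachial index and laboratory tests, including "Iron profile (Hemoglobin, MCV, hematocrit, ferritin, TSAT". No medication item.
- **12 months.** Laboratory tests, now with hepcidin and erythropoietin, plus ECG, echocardiography and CT. No medication item.
- **Statistical Analysis.** "the Mann-Whitney test and the unpaired t-test will be used for comparisons of means of two quantitative variables", with chi-square or Fisher tests for frequencies and Kaplan-Meier for survival. There is no covariate adjustment and no rule for treatment started during follow-up.

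**The concern.** ESA, iron and transfusion all act on the quantities that make up the anaemia outcome. Iron changes ferritin, TSAT and hepcidin directly. A serum erythropoietin value taken on an ESA no longer shows what the patient is producing. If the drug reduces the need for such treatment, use will differ between arms after randomisation, and a difference in a marker at 12 months could come from dapagliflozin, from the co-treatment, or from both.

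Hepcidin and erythropoietin are sampled only at baseline and 12 months. There is no intermediate value to fall back on if treatment begins between those samples.

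At stake is the reading of an objective that the Rationale presents as the trial's novelty. The renal composite does not depend on these markers.

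**Working it through.** **1. Is there anything to reproduce?** The only planning figure is about 98 patients at α 0.05 and 80% power. No effect size, SD, event rate or sidedness is given, so it cannot be rebuilt, and it is not tied to haemoglobin. It has no bearing here.

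**2. Expected versus planned.** The Introduction reports fewer starts of anaemia treatment on an SGLT2 inhibitor and names hepcidin, iron availability and erythropoietin as the pathway. Methods measures those markers but asks about drugs once, before treatment starts. Statistical Analysis compares two groups and stops there. Nothing in the document links the first of these to the other two.

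**3. Illustration for haemoglobin.** All inputs are assumptions except 50 per arm and α 0.05 (taken as two-sided). True difference without co-treatment 0.8 g/dL; SD 1.5 g/dL.

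- Standard error = 1.5 × √(2/50) = 0.30 g/dL.
- Observed difference = 0.8 − (excess share of controls treated) × (gain per treated patient).
- Power is from the two-sample t-test.

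| Treated, control vs dapagliflozin | Gain (g/dL) | Observed difference (g/dL) | Power |
|---|---|---|---|
| no imbalance | – | 0.80 | 75% |
| 5-point excess | 1.0 | 0.80 − 0.05 = 0.75 | 70% |
| 15% vs 5% | 1.0 | 0.80 − 0.10 = 0.70 | 64% |
| 25% vs 10% | 1.0 | 0.80 − 0.15 = 0.65 | 57% |
| 25% vs 10% | 1.5 | 0.80 − 0.225 = 0.575 | 48% |

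Over a wider grid (SD 1.2 to 1.8, true difference 0.5 to 0.9 g/dL, gain 1.0 to 1.5 g/dL, normal approximation), a 20-point imbalance takes power from 28–96% to 8–83%. The direction is the same throughout; the size depends on the inputs.

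**4. Would dropping the treated samples solve it?** This is tested on the haemoglobin scale as an analogue, with the same 0.8 g/dL, SD 1.5 and 25% vs 10% treated. If the treated share p is chosen by a normal variable with correlation ρ to the outcome, low values being treated, the mean of those left rises by ρ × SD × φ(z_p)/(1 − p).

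- Control, p = 0.25: 1.5 × 0.3178/0.75 = 0.636 (times ρ).
- Dapagliflozin, p = 0.10: 1.5 × 0.1755/0.90 = 0.292 (times ρ).
- Remaining difference = 0.8 − ρ × 0.343.

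This gives 0.70 at ρ = 0.3, 0.56 at ρ = 0.7 and 0.46 if the lowest values are always the ones treated. Exclusion can therefore be at least as biased as leaving the co-treatment in (0.65 to 0.575 in the same scenario).

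**The case against.** The strongest reply is that randomisation already protects the comparison. A contrast of arms regardless of co-treatment answers a legitimate question, and more treatment among controls would make a positive haemoglobin result harder, not easier, to obtain. This stands for haemoglobin. What remains is that the plan does not say this is its intended question. For erythropoietin and the iron markers, the same contrast cannot be read as an effect on the patient's own production or iron handling.

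A reader might also infer stronger things that the documents do not support:

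- **That co-treatment will not be recorded.** The follow-up lists are headed as investigations. They also omit hypoglycaemia, serious adverse events and end-stage kidney disease, all of which are planned outcomes, so they are not a full data-capture form. The supported statement is that recording is not specified.
- **That the protocol predicts an imbalance in this trial.** The cited result is post hoc, from another SGLT2 inhibitor in type 2 diabetes, and diabetes is excluded here. It makes an imbalance plausible, no more. Eligibility does not require anaemia and allows eGFR up to 75, so anaemia treatment may be uncommon.
- **That unadjusted follow-up values will be compared.** The text does not say whether the tests use values or changes. It calls bivariate methods the initial evaluation, although it describes no later step.
- **That the erythropoietin or ferritin contrast would reverse.** Nothing in the documents establishes this. The direction depends on which treatment is given and to whom.

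**Conclusion.** The concern holds in a limited form. Recording of ESA, iron and transfusion after baseline is not specified, nor is their handling in the anaemia outcome, although the background gives reason to expect that their use could differ by arm. If these data are not collected, the erythropoietin, hepcidin, ferritin and TSAT contrasts cannot be interpreted, and no later analysis can repair that. The all-randomised haemoglobin comparison remains valid and is probably conservative, provided controls are treated at least as often as patients on dapagliflozin.

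The haemoglobin effect, SD, treatment rates and gain are all assumed, so the power losses above show direction and plausible scale only. The primary renal outcome is untouched. This is a change that should be made, not one on which the trial's main conclusion depends.

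**What to change.** 1. Record ESA, iron (oral or IV) and transfusion at baseline and at every 3-monthly visit, with dates and enough detail to recognise escalation.
2. Make 12-month haemoglobin, adjusted for baseline haemoglobin, in all randomised patients and regardless of co-treatment, the main anaemia analysis in place of the unadjusted test.
3. Report the number starting anaemia treatment in each arm.
4. Add one supplementary haemoglobin analysis. Either give start or escalation of anaemia treatment the worst rank, or model the values after it and state the assumption.
5. For erythropoietin, ferritin, TSAT and hepcidin, keep all randomised patients in the main comparison and show results by co-treatment status descriptively only. Excluding post-ESA or post-iron samples should not be the main analysis, because it selects on an event after randomisation that the drug may influence.

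The cost is one more item on an existing visit form, a few lines of analysis text, and a supplementary result that relies on an assumption. Patient care is unchanged.

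### Erythropoietin is a named secondary outcome but hepcidin is not, although both are measured twice; the plan describes no baseline adjustment for either, and erythropoietin alone is hard to read

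*Combined protocol and SAP*

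**What the plan says.** The Introduction gives two mechanisms for an effect on anaemia. The first is that "there are data suggesting SGLT2i acts by inhibiting hepcidin, which will increase iron bioavailability and red blood cell production". The second is medullary hypoxia, which "increases the level of hypoxia inducible factor (HIF) and increase erythropoietin production".

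The laboratory lists in the Methods include "Serum hepcidin level" and "Serum erythropoietin level" at baseline and again at 12 months, both under the iron profile tests. The three-monthly panel has haemoglobin, MCV, haematocrit, ferritin and TSAT, but neither of these two markers.

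Under Secondary outcome measures the relevant line is "Effect of Dapagliflozin on anemia & erythropoietin level". It names no time point, scale or expected direction. Hepcidin appears in no outcome.

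For quantitative variables, the Statistical Analysis section says that "the Mann-Whitney test and the unpaired t-test will be used for comparisons of means of two quantitative variables". It describes no adjustment for baseline and no rule for choosing between the two tests. It does not say whether the 12-month value or the change is compared, or how erythropoietin is to be read alongside haemoglobin.

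**The concern.** Two things look wrong.

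- **Unused information.** Each patient has a baseline value of both markers, but the described tests make no provision for it. Hepcidin, which the plan puts forward as one of its two mechanisms, is assayed twice and tied to no outcome.
- **Ambiguous direction.** The plan's second mechanism raises erythropoietin. If a higher haemoglobin in turn lowers erythropoietin, the first mechanism would push it down. The 12-month level is then the net of two opposing effects, and neither direction is plainly favourable.

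At stake is the reading of a named secondary outcome. An unchanged or lower erythropoietin could be reported as no effect when haemoglobin has in fact risen.

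**Working it through.** **1. The plan's own figure.** There is no calculation for erythropoietin. The only sample-size figure is about 98 patients at alpha 0.05 and 80% power, attributed to DAPA-CKD. It cannot be reproduced, because no effect size, SD, event rate or sidedness is given. Back-solving for a two-sided comparison of means with 49 per arm gives d = (1.960 + 0.842) × √(2/49) = 0.566, or 0.572 with the noncentral t. Nothing below depends on it.

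**2. Inputs.** From the plan: 50 per arm and a threshold of 0.05, taken as two-sided. Assumed, with no source in the documents:
- haemoglobin gain g = 0.5 to 0.8 g/dL
- feedback slope b = 0.1 to 0.3 log units of erythropoietin per g/dL
- direct HIF-driven rise D = 0, 10% or 20%
- SD of ln(erythropoietin) = 0.6

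**3. Net effect.** Net log difference = ln(1 + D) − b × g.

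| D | Smallest feedback (0.1 × 0.5 = 0.05) | Largest feedback (0.3 × 0.8 = 0.24) |
|---|---|---|
| 0 | −0.05, or −5% | −0.24, or −21% |
| 10% | 0.095 − 0.05 = 0.045, or +5% | 0.095 − 0.24 = −0.145, or −13% |
| 20% | 0.182 − 0.05 = 0.132, or +14% | 0.182 − 0.24 = −0.058, or −6% |

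There are six combinations of b (0.1, 0.2, 0.3) and g (0.5, 0.8), with products 0.05, 0.08, 0.10, 0.16, 0.15 and 0.24. At D = 20%, five of the six leave the net positive. At D = 10%, two do, and one of the other four is almost exactly null (0.0953 − 0.10 = −0.005).

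**4. Power for a 20% direct rise.** SE = 0.6 × √(2/50) = 0.12.
- No feedback: 0.182/0.12 = 1.52, and Φ(1.52 − 1.96) = 0.33.
- Smallest feedback: 0.132/0.12 = 1.10, power about 20%.
- b = 0.2 and g = 0.8: (0.182 − 0.16)/0.12 = 0.19, power about 5%.

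Even without feedback, 80% power at 50 per arm needs about 0.566 × 0.6 = 0.34 log units, a rise of about 40%.

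**5. A second set of assumptions.** Take direct effects h = 0.1, 0.2 or 0.3 log units, the same slopes, and g = 0.5 or 1.0 g/dL. Of the 18 combinations, 10 give a positive net, 4 are exactly null and 4 are reversed (ratio 0.82 to 0.95). With h = 0, all six are reversed (0.74 to 0.95). Power for the positive ones runs from 0.06 to 0.87 at log SD 0.4 to 0.6.

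**6. Can a null coexist with benefit?** With h = 0.2, b = 0.2 and g = 1.0, the net is 0.2 − 0.2 × 1.0 = 0. The ratio is 1.00 and the test rejects only at its 5% error rate. The same 1.0 g/dL haemoglobin gain would be detected with power 0.91 to 0.98 at an assumed SD of 1.5 to 1.2 g/dL. At a gain of 0.5 g/dL, haemoglobin power is itself only 0.38 to 0.54.

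**7. Baseline adjustment.** Let σ be the SD at each time, ρ the baseline-to-12-month correlation and n the number per arm. The variance of the arm difference is approximately:
- 12-month value: 2σ²/n
- change: 4σ²(1 − ρ)/n
- ANCOVA: 2σ²(1 − ρ²)/n

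Since 1 − ρ² ≤ 1 and (1 − ρ)(1 + ρ) ≤ 2(1 − ρ), ANCOVA is at least as precise as either, apart from one degree of freedom. The documents give no ρ, so no numerical gain is claimed.

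**The case against.** The strongest reply is that the opposing-direction argument is not in the documents. They give one direction for erythropoietin, upward through HIF. The downward feedback is general physiology, and every slope, gain and SD above is assumed. This stands. A reader might infer that a working drug must leave erythropoietin null or reversed. The documents do not support that, and on the assumed ranges many combinations stay positive, including five of six with a 20% direct rise. Because power for that rise is only 33% with no feedback, a null result would be likely in any case.

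A reader might also infer that the anaemia question is lost or rests on erythropoietin. It does not. Anaemia is named in the same outcome line, haemoglobin is measured every 3 months, and the plan attaches no success rule to erythropoietin.

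Nor do the documents show that hepcidin would go unanalysed. The Methods state that the listed data are to be evaluated as well as collected. Anaemia is undefined and could be read to cover the whole iron panel, and ferritin and TSAT already bear on iron availability. Hepcidin being mentioned first is order of mention, not priority.

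What remains is that only one of the two proposed mechanistic markers is a named outcome, and that the described analysis makes no provision for the baseline values.

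**Conclusion.** The point holds as a minor one. The absence of hepcidin from the outcomes and of any baseline adjustment from the analysis can be read directly from the plan. The difficulty in reading erythropoietin is conditional on negative feedback from haemoglobin. If that exists, a net change anywhere from −21% to +14% is compatible with a haemoglobin gain of 0.5 to 0.8 g/dL on the assumed inputs. The result is possible, not inevitable.

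Baseline adjustment improves precision but does not separate the two pathways. That ambiguity is handled by reporting the markers together. The primary outcome, the randomised haemoglobin comparison and the safety outcomes are unaffected.

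**What to change.** - In the Statistical Analysis section, specify that 12-month ln(erythropoietin) and ln(hepcidin) are compared between arms by ANCOVA adjusted for the log baseline value of the same marker, and reported as ratios with confidence intervals.
- In the outcome list, name hepcidin as a secondary or exploratory marker, and give 12 months as the time point for both.
- State that both are reported beside the haemoglobin difference, and that a lower erythropoietin is not in itself evidence of no effect.

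A further step would be to compare arms on the ratio of observed erythropoietin to the level predicted from haemoglobin, using a line fitted at baseline. Leave this out or label it exploratory. A between-patient line across eGFR 20-75 may be confounded by kidney function, and the prediction would use post-randomisation haemoglobin.

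The change needs no new visit, sample or assay. Its cost is one more marker comparison in a plan that judges every test at p ≤ 0.05. Labelling hepcidin exploratory limits the weight placed on that comparison.

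### Safety is part of a superiority question but is judged only by p ≤ 0.05, with no effect estimate or interval, so at 50 per arm a non-significant result could hide a material excess of harm

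*Combined protocol and SAP*

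**What the plan says.** Under Research questions, the main question is whether the drug shows "superiority over conventional lines of treatment of chronic kidney disease as regard to efficacy and safety". Safety therefore sits inside a superiority question. The Objectives section makes no separate safety claim.

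Under Outcomes, the last secondary outcome is "Safety of Dapagliflozin regarding the number of hypoglycemia episodes between groups and serious adverse events". The plan does not say whether patients with an event or episodes are to be counted, and it does not define a serious adverse event.

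The Statistical Analysis section has no part for safety. Its general rules are:

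- for display, "Qualitative data will be displayed in cross tabulations", with means and standard deviations for quantitative data;
- for testing, "the chi-square and Fisher's exact tests will be used for comparisons of frequencies of qualitative variables", and Mann-Whitney or unpaired t-tests for quantitative variables;
- for decision, "A p-value ≤ 0.05 is considered significant".

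No between-group effect estimate or confidence interval is planned for any contrast. Kaplan-Meier is named only for patient survival. There is no assumed risk of an event, no safety margin and no power statement for safety. There are 50 patients per arm (Patients' enrollment), followed for 12 months.

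**The concern.** A superiority test can end in two ways. If it is significant, one arm had more events. If it is not, the test says nothing about how large an excess the data still allow. The second ending needs an interval, and the plan provides none.

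This matters because the arms are small, and serious events and hypoglycaemia in non-diabetic patients may be uncommon. The safety half of the main question could close on a non-significant p-value that a reader takes as reassurance, while the data remain compatible with a sizeable excess on dapagliflozin.

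A second difficulty lies in the testing rule. Chi-square and Fisher's exact test are both named without saying when each applies. At these counts they can disagree, so the same table could be called significant or not.

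**Working it through.** **Inputs.** From the documents: 50 per arm and a 0.05 threshold, with Fisher and chi-square as the tests of frequencies. Assumed, because the documents are silent: two-sided tests, no continuity correction for chi-square, patients with at least one event as the unit, and a range of event risks.

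**The plan's own figure.** The sample size "was calculated based on previous research by (DAPA-CKD"), "using G. power program with α error 0.05 and power 80% and it was equal to approximately 98 patients". No endpoint, test or effect is given, so 98 cannot be reproduced. Solving backwards with 49 per arm and 80% power, two-sided, gives a standardised mean difference of about 0.57 (t-test), or pairs of proportions such as 5% v 25%, 10% v 33% or 20% v 46%. Nothing in the documents selects among these or links the number to safety.

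**Step 1: power at 50 v 50.** Power = Σ over a, b of Bin(a; 50, p_T) × Bin(b; 50, p_C) × 1{p-value(a, b) ≤ 0.05}.

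| Control v dapagliflozin risk (assumed) | Fisher | Uncorrected chi-square |
|---|---|---|
| 5% v 10% | 6.3% | 14.5% |
| 10% v 20% | 19.5% | 30.3% |
| 20% v 40% | 51.5% | 59.5% |
| 10% v 30% | 64.0% | 73.4% |
| 30% v 60% | 82.9% | 87.6% |

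So a true doubling from a control risk of 5% to 20% is missed between about 40% (100 - 59.5) and 94% (100 - 6.3) of the time. A tripling from 10% is usually found.

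**Step 2: observed splits.** Chi-square: z = ((a - b)/50) / √(p̄(1 - p̄) × 2/50), with p̄ = (a + b)/100.

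- 7 v 2: p̄ = 0.09, z = 0.10/0.0572 = 1.75, p = 0.08; Fisher p = 0.16.
- 12 v 5: p̄ = 0.17, z = 0.14/0.0751 = 1.86, p = 0.06; Fisher p = 0.11.
- 9 v 2: p̄ = 0.11, z = 0.14/0.0626 = 2.24, p = 0.025; Fisher p = 0.051.

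The first two are non-significant by both tests. The third changes verdict with the test. So does 10 v 3 (Fisher 0.071, chi-square 0.037).

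**Step 3: what an interval would show.** Newcombe limits for d = p1 - p2, from the Wilson limits (l, u) of each arm: lower = d - √((p1 - l1)² + (u2 - p2)²); upper = d + √((u1 - p1)² + (p2 - l2)²).

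For 7 v 2, the Wilson limits are 0.0695 to 0.2619 and 0.0110 to 0.1346.

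- Lower: 0.10 - √(0.0705² + 0.0946²) = 0.10 - 0.118 = -0.018.
- Upper: 0.10 + √(0.1219² + 0.0290²) = 0.10 + 0.125 = +0.225.

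The result is +10 points (-1.8 to +22.5). By the same formula, 12 v 5 gives +14 points (-0.9 to +28.6). Both results would be labelled non-significant, although their intervals reach an excess above 20 points.

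**Step 4: no events.** With 0 of 50, the upper limit of the two-sided exact 95% interval is 1 - 0.025^(1/50) = 7.1%.

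**The case against.** Four arguments can be made for the plan.

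*It never says that p > 0.05 means safe.* This is true. The bivariate tests are introduced as an initial evaluation, and cross tabulations would put the counts in view. The misreading would be the reader's. But no later step is named, counts alone do not show what excess remains possible, and no other criterion is offered.

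*Large excesses would be detected.* This is also true in the main. A reader might infer from the low power that the safety comparison will nearly always end as non-significant. The figures do not support that: 10% v 30% is found 64% to 73% of the time and 30% v 60% more than 80% of the time. All these risks are assumed.

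*Superiority in safety is a coherent aim.* A reader might think that an added drug cannot be expected to lower adverse events. The documents do not support so flat a statement. The Introduction cites less worsening of kidney function and fewer heart-failure hospitalisations with this class (the latter mainly in type 2 diabetes), and such events could count as serious adverse events. The problem is not that the hypothesis is absurd, but that failing to confirm it says little about safety.

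*Repeated episodes can be handled.* A reader might suppose that group totals of hypoglycaemia episodes will be tested as though episodes were independent. The plan does not say so. Its Mann-Whitney and t-tests could be applied to episodes per patient, which keeps the patient as the unit. What stands is that the unit is not named.

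**Conclusion.** The concern holds in this form: safety is placed in a superiority question, the only stated criterion is a p-value, and at 50 per arm a non-significant p-value could conceal a material excess of harm. For a doubling from a 5% to 20% control risk, power runs from 6.3% to 59.5% across the two named tests. Splits of 7 v 2 and 12 v 5 pass as non-significant by either. The lack of a rule for choosing between the tests makes the verdict arbitrary for splits such as 9 v 2.

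This rests on assumed risks, two-sided tests, patients as the unit and no dropout. It does not show that the trial will miss harm, or that the sponsor intends to equate non-significance with safety. It concerns the interpretation of a secondary outcome that forms part of the main question, and leaves the primary analysis untouched. It should be put right before the data are analysed.

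**What to change.** In the Statistical Analysis section, add a short safety paragraph:

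1. For serious adverse events and for hypoglycaemia, the main safety result is the number of patients with at least one event in each arm and the risk difference with a 95% confidence interval, by one named method (Newcombe or exact).
2. Hypoglycaemia episodes are summarised, and compared if at all, per patient and not as group totals.
3. A p-value above 0.05 will not be reported as evidence of safety.

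Under Research questions, reword the main question to superior efficacy, with safety estimated.

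No particular count model needs to be imposed. The change costs a few sentences and needs no new data or patients. The downside is a more modest safety conclusion: the intervals will be wide, as the 7 v 2 example shows.
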